additional preoperative educational materials or resources other than what is currently provided by their care team. This usually includes a routine phone call, text, or email from a pre-operative staff member within a few days of the child's scheduled procedure to provide basic information about fasting, when to arrive at the hospital, and anything additional that needs to be done prior to the procedure (e.g. COVID-19 testing), when applicable. Any specific information about the anesthetic will be deferred to the anesthesia team for the surgical day, per usual.

In both the intervention and control groups, if parents specifically request additional information to prepare for surgery, pre-op staff may send them the "Social Story" developed by the Autism Spectrum Center, Child Life Services, and Waltham Surgical Services. This document provides an age-appropriate step-by-step guide as to what to do and what to expect on the day of surgery.

On the day of surgery, all parents participating in the study, regardless of group assignment, will receive surveys to complete in the pre-operative holding area via REDCap®. The surveys will be given to the parent who consented to the study. If both parents are present, and both consented to the study, they will both receive surveys to complete. A research staff member trained for reliability and blinded to the study arm will assess the child for signs of anxiety in the pre-op holding area.

For both groups, once the surgical procedure is complete, and the child has gone to the PACU, Emergence Agitation/Delirium will be assessed per standard of care at Waltham by the bedside PACU nurse using the Pediatric Agitation Emergence Delirium Scale (PAED). The

research team will collect this PAED information retrospectively from the child's electronic medical record.

(4) Definition of Primary and Secondary Outcomes/Endpoints:

See Table 1 for Summary of Outcomes/Measures

Patient Demographics

Parental age, gender, ethnicity, and highest education level achieved will be collected as part of the REDCap® preoperative survey to better understand the pilot group and educational needs (Appendix B).

Primary Outcomes

Parental Utilization:

- *When provided with the opportunity to obtain more information as it relates to the perioperative experience, do parents and their children use the tool?*
- *How many times did they access the tool and for how long?*
- *Were there any barriers to accessing the PIRA tool?*

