If there were problems surrounding the accessibility, content, language, or any other system issues, this will affect utilization and the PIRAs future potential impact.

Regardless of the medium, materials, or content provided, no preoperative educational program can be successful and sustainable unless readily adopted and utilized by parents and children. As such, a primary outcome will evaluate whether families actually viewed the materials, with whom, and how much time they spent with the PIRA.

Parental Perceived Impact and Impressions:

- *Did parents find the tool subjectively helpful?*
- *What improvements or changes in content or language would they consider?*
- *Would parents recommend the PIRA to future families?*

Identifying parental perceived benefits or drawbacks to the PIRA may elucidate the familial interactions and how they feel about their educational experience in a different way than anxiety or other objective data. Similarly, given the novel nature of the PIRA, it is important to identify any educational gaps and potential for future topics and educational needs. If parents believe the PIRA improved their preoperative experience, it could be useful for future families.

Secondary Outcomes

Child Anxiety in Preoperative Waiting:

As discussed, more than 60% of pediatric patients have been found to suffer from anxiety in the preoperative period. The effects of anxiety may have behavioral sequelae, or Postoperative Maladaptive Behaviors (POMB), which can last up to a year or longer. Therefore, reducing anxiety levels should be a priority of any educational tool for pediatrics. Numerous randomized control trials have demonstrated decreased child anxiety in preoperative waiting for those patients who participated in preoperative educational programs including videos, tours, apps, games, and books. *Is there a similar difference in the control and intervention groups' preoperative anxiety with this PIRA intervention?*

Parental Anxiety in Preoperative Waiting:

In several cited studies, parental anxiety directly correlates with the pediatric patient's anxiety. Thus limiting or reducing parental anxiety is an important part of a preoperative education intervention. *Does improved communication and education decrease parental anxiety?* An intervention which serves to improve communication between the parent/child as well as the parent/anesthesia provider AND reduce parental anxiety would perhaps provide significant benefits.

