Appendix B. Parental PIRA Survey

Please complete the survey, below. Your responses to the following questions will better help us to understand how to improve our preoperative education and communication for parents and their children. As a study participant, you were randomly assigned to either receive an online interactive tool focused on educating children, named PIRA, or you received our standard preoperative information. If any of the below questions make you uncomfortable, please leave them blank.

Demographics:

Q1. Your current age (in years):

Q2. Gender:

Q3. Ethnicity:

Q4. Highest level of education achieved:

Pre-Operative Education Experience:

Q1. What of the following statements describes your experience with the anesthesia education agent, Ira? (Select all that apply)

- I did not receive the link to Ira
- I received the link to Ira, but did not watch it
- I received the link to Ira, but a different care provider or family member watched Ira.
- I watched Ira WITHOUT my child
- I watched Ira WITH my child
- I had a hard time using Ira
- My child liked using or watching Ira
- My child seemed LESS stressed about surgery or anesthesia because they watched Ira
- My child seemed MORE stressed about surgery or anesthesia because they watched Ira
- I understood anesthesia better after watching Ira
- Ira helped me talk to my child about anesthesia and surgery
- Ira helped answer questions about anesthesia
- I felt less stressed about surgery or anesthesia because I watched Ira
- Ira made my surgery experience BETTER
- Ira made my surgery experience WORSE

- Ira was difficult to use or understand

Q2. In total, about how long did you spend with the interactive education agent, Ira?

- Less than 5 minutes
- 5-30 minutes
- 30-60 minutes
- More than 60 minutes
- I did not view the agent

Q3. How likely are you to recommend the interactive education agent, Ira, to future families? (Skip if you did not receive or view Ira)

This is a sliding scale

0 = Not at all Likely to Recommend-----100 = Extremely likely to recommend

Q4. Write any topics that were missing, unclear, or absent from the interactive education agent, Ira. (Skip if you did not receive or view Ira)

**Free Text Response_____

Q5. Write any suggestions for future improvements to the interactive education agent, Ira. This may include any difficulties in accessing or using it. (Skip if you did not receive Ira)

**Free Text Response_____

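### In Appendix B question 1, two tick lines overlap on difficulty of use and the second also covers difficulty understanding, so the ticks give no separate comprehension proportion and no unambiguous usability proportion

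*Combined protocol and SAP*

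**What the plan says.** Among the primary outcomes, section D(4) poses a question under Parental Utilization: "Were there any barriers to accessing the PIRA tool". It then explains why the answer matters: "If there were problems surrounding the accessibility, content, language, or any other system issues, this will affect utilization". Aim 2 in section A likewise includes issues that parents met with the tool.

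The instrument is Appendix B. Question 1 of its Pre-Operative Education Experience block is marked "Select all that apply". Among its options are:

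- "I had a hard time using Ira"
- "Ira was difficult to use or understand"
- "I did not receive the link to Ira"

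Two free-text questions follow. Question 4 says "Write any topics that were missing, unclear, or absent from the interactive education agent, Ira". Question 5 asks for suggested improvements and adds "This may include any difficulties in accessing or using it".

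Section H plans generic summary statistics for quantitative survey data and a thematic summary for free text. It does not say how question 1 options are to be counted or combined.

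**The concern.** Two options in one list describe the same event, trouble using the tool, and one of them also describes a second event, trouble understanding it. A parent with a technical problem can truthfully tick the first line, the last line or both. A parent who found the words too hard has only the last line, which reads equally as a usability complaint.

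What is at stake is how useful the pilot's feedback will be. Section B describes adjusting the tool on user feedback as essential. A software fault and a script fault call for different repairs. Both are plausible: Appendix A limits access to one browser on a computer or tablet and warns that progress is not saved, while the content has to suit children aged 4 through 10.

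**Working it through.** The plan states no barrier or difficulty rate, so there is no figure to reproduce. The check asks what the two ticks can and cannot show.

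**Inputs from the plan.** Section I gives 30 per group for analysis and 38 per group recruited (30/(1 − 0.20) = 37.5, rounded up). Neither is exactly the number of survey respondents, because section D(3) lets both consenting parents complete surveys. Tick counts and true rates below are assumptions.

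**Step 1: dependence on the counting rule.** Let *a* parents tick the first line and *b* the last, out of *n*. Either line lies between max(*a*, *b*)/*n* and min(*n*, *a*+*b*)/*n*. Both lines lies between max(0, *a*+*b*−*n*)/*n* and min(*a*, *b*)/*n*.

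| Assumed *n*; *a*, *b* | First line | Last line | Either | Both |
|---|---|---|---|---|
| 30; 3, 6 | 10% | 20% | 20–30% | 0–10% |
| 30; 6, 6 | 20% | 20% | 20–40% | 0–20% |
| 38; 3, 6 | 7.9% | 15.8% | 15.8–23.7% | 0–7.9% |

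Once data are in, a cross-tabulation fixes the last two columns. It does not reveal what a tick on the last line meant.

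**Step 2: what stays unknown.** Assume true usability difficulty *u* = 0.20 and true comprehension difficulty *c* = 0.10, independent. Let parents with usability difficulty split equally between first line only, last line only and both.

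- First line: 0.20 × 2/3 = 13.3%
- Last line: 1 − (1 − 0.20 × 2/3)(1 − 0.10) = 1 − 0.8667 × 0.90 = 22.0%
- Either line: 0.20 + 0.10 − 0.02 = 28.0%
- Sum of the lines: 35.3%, which counts parents who tick both twice

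The first line contains no comprehension term; it is under-counted, not mixed. The last line is mixed. Its 22% lies near 20% only because missed usability cases and added comprehension cases roughly cancel. With *u* = *c* = 0.10 the lines show 0.10 × 2/3 = 6.7% and 1 − 0.9333 × 0.90 = 16.0%.

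**Step 3: identifiability.** The two ticks give three free cell proportions (first only, last only, both). Even under independence there are four unknowns: *u*, *c* and two ticking probabilities. Now drop independence and suppose that every tick is truthful and every parent with a difficulty ticks at least one line covering it. In the *u* = 0.20 example the data then bound usability difficulty only between the first-line rate and the either-line rate, 13.3% to 28.0% (about 5 to 11 of 38). Comprehension difficulty is bounded only between 0 and the last-line rate, 0 to 22.0% (0 to about 8 of 38). No later analysis of these ticks alone narrows those ranges.

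**Step 4: what the other items add.** Question 4 is about topics, so it reaches content gaps and unclear content, but only indirectly whether the wording was too hard. Question 5 reaches access and use. Neither asks about language as such. Both are summarised as themes, and a blank does not mean that there was no difficulty. The timestamped clicks in section D(5) show use, not why a family struggled.

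**The case against.** The strongest reply is that this is questionnaire wording in a pilot's descriptive summary, and that the plan separates the causes elsewhere. Questions 4 and 5 ask about content and about access or use in different places. Table 1 makes gaps and recommendations for later versions a primary outcome measured by free text, and section G has at least two team members analyse it. Not receiving the link has its own option. Families with access problems are directed to the investigator, and the programming team monitors technical faults. Much of this stands: free text can guide the next version. It does not supply a proportion for comprehension difficulty, and the ticks cannot.

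Three stronger readings are tempting, and the documents do not support them.

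- A reader might infer that a primary barrier-rate endpoint is defined twice. Section D(4) poses barriers as a descriptive question. Neither it nor section H nor Table 1 gives a rate, numerator, denominator or threshold, and the two lines are response options.
- A reader might infer that the protocol requires accessibility to be measured apart from content and language. Section D(4) lists these together as things that affect utilization and does not require separate measurement.
- A reader might infer that the survey cannot tell usability from content at all. That is true of the last line and limits the question 1 ticks; it is not true of the survey as a whole.

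It is also fair to say that counting either line gives a coherent any-difficulty rate, and that sampling error is large here: 6 of 30 has an exact 95% interval of 7.7% to 38.6%. But the ambiguity is one of meaning, and more respondents would not remove it.

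**Conclusion.** The point holds, at minor severity. The two lines overlap on difficulty of use, the last also covers understanding, no tick-box isolates understanding, and no counting rule is given. A comprehension proportion cannot be obtained from question 1, and a usability proportion depends on the line or combination counted.

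The overlap and the missing rule can be read directly in Appendix B and section H and need no assumption. The size does: 10%, 20% or 20–30% for the same 30 parents follows from assumed counts of 3 and 6, and the 13–28% and 0–22% bounds follow from assumed true rates and ticking behaviour. The documents give none of these.

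The effect is confined to descriptive reporting of encountered issues and barriers under the primary outcomes. The mYPAS comparison on which the sample size rests is untouched, as are the usage logs and the recommendation score.

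**What to change.** Keep "I had a hard time using Ira" for technical or usability problems. Change the last option to: *Ira was difficult to understand (words or content)*.

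State in section H that the two are tabulated separately, with two denominators: all surveyed PIRA-arm parents, including any who tried but could not open the tool, and those who viewed it. Using only the second would drop the families whose access failed, which is what section D(4) asks about. Restricting to the PIRA arm matters because both arms receive the same survey.

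The cost is a one-line edit to the REDCap form and a sentence in the analysis plan. If data collection has begun, parents already surveyed must be reported under the old wording and not pooled with later ones. Show them as a cross-tabulation of the two lines, with neither line labelled a usability rate.

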The amount of time spent using the PIRA and the number of times the PIRA was accessed will be able to be collected via the program itself, stored on a secure Northeastern University Server, and will be accessible only to the study team. Each click of the mouse a user makes in the system will be timestamped and saved on the database. This information will be de-identified. Additionally, the parental survey administered by the research team member in the preoperative holding area will obtain self-reported data on PIRA access and time spent using the tool (Appendix B).

Parental perceived impact and impressions:

This outcome will be assessed in the same survey (Appendix B) as Parental Utilization. The survey will have no identifying questions and will be automatically uploaded to REDCap®, accessible only to members of the research team. Any data will be de-identified and presented in aggregate.

Secondary Outcomes Data

Child Anxiety in Preoperative Waiting:

Child anxiety will be assessed using the modified Yale Preoperative Anxiety Scale (mYPAS), an observational state anxiety measure for children containing 27 items in five categories (activity, emotional expressivity, state of arousal, vocalization, and use of parents). See Figure 1. The mYPAS has been validated for measuring childrens' anxiety (Kain et al., 1995; Kain et al., 1997). Members of the research team who will administer the mYPAS for this study will be trained for reliability. mYPAS scores range from 22.5 to 100, with higher scores indicating more anxiety.

Parental Anxiety in Preoperative Waiting:

Parental anxiety will be assessed using the State-Trait Anxiety Inventory (STAI). See Figure 2. This self-report anxiety instrument contains two separate 20-item subscales that measure trait (baseline) and state (situational) anxiety (Spielberger, 1973; Spielberger, 1983; Spielberger, 1989) This survey will take place in the preoperative holding area and will be administered in conjunction with the previous utilization/recommendation survey (Appendix B). The STAI is scored from 20-80, with higher scores indicating more anxiety.

Emergence from Anesthesia: Presence or absence of emergence agitation/delirium

(ED):

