Q6. Self-evaluation questionnaire. Rate the following statements how they apply to you from 1 = Not at all to 4 = Very Much So

	1 = Not at all	2 = So me wh at	3 = Mo der y at	4 = Ver atel ch so
I feel calm				
I feel secure				
I am tense				
I feel strained				

I feel at
ease

I feel
upset

I am
presently
worrying
over
possible
misfortu
nes

I feel
satisfied

I feel
frightene
d

I feel
comforta
ble

I feel
self-
confiden
t

I feel
nervous

I am
jittery

I feel
indecisiv
e

I am
relaxed

I feel
content

I am
worried

I feel
confused

I feel steady	
I feel pleasant	

Figure 1. Modified Yale Preoperative Anxiety Scale (mYPAS) for Child Anxiety

Domain: Activity

1. Looking around, curious, playing with toys, reading (or other age-appropriate behavior); moves around holding area/treatment room to get toys or go to parent; may move toward OR equipment
2. Not exploring or playing, may look down, may fidget with hands or suck thumb (blanket); may sit close to parent while waiting, or play has a definite manic quality
3. Moving from toy to parent in unfocused manner, non-activity-derived movements, frenetic/frenzied movement or play; squirming, moving on table, may push mask away
4. Actively trying to get away, pushes with feet and arms, may move whole body; in waiting room, running around unfocused, not looking at toys or will not separate from parent

Domain: Vocalizations

1. Reading (nonvocalizing appropriate to activity), asking questions, making comments, babbling, laughing, readily answers questions but may be generally quiet; child too young to talk in social situations or too engrossed in play to respond
2. Responding to adults but whispers, "baby talk," only head nodding
3. Quiet, no sounds or responses to adults
4. Whimpering, moaning, groaning, silently crying
5. Crying or may be screaming "no"
6. Crying, screaming loudly, sustained (audible through mask)

Domain: Emotional Expressivity

1. Manifestly happy, smiling, or concentrating on play
2. Neutral, no visible expression on face
3. Worried (sad) to frightened, sad, worried, or tearful eyes
4. Distressed, crying, extremely upset, may have wide eyes

Domain: State of Apparent Arousal

1. Alert, looks around occasionally, notices/watches anesthesiologist (could be relaxed)
2. Withdrawn child sitting still and quiet, may be sucking on thumb or face turned in to adult
3. Vigilant looking quickly all around, may startle to sounds, eyes wide, body tense

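### The parental STAI comes last in Appendix B, so the questions leading into the Aim 3 parental anxiety comparison differ by arm

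*Combined protocol and SAP*

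**What the plan says.** Section A (Aim 3) asks for the difference in parental preoperative anxiety between the PIRA and control groups. Section D(4) and Table 1 list it as a secondary outcome, measured by the STAI. Under D(5), parents in both arms complete the same survey in the preoperative holding area, and the STAI is given together with the utilization and recommendation questions.

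Appendix B fixes the printed order:

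- The introduction tells every parent that "you were randomly assigned to either receive an online interactive tool focused on educating children, named PIRA, or you received our standard preoperative information". It ends with "If any of the below questions make you uncomfortable, please leave them blank".
- Four demographic questions follow.
- Then come five Ira items, Q1 to Q5. Q1 offers 16 statements, the first being "I did not receive the link to Ira". Q2 asks for time spent and includes "I did not view the agent". Q3 and Q4 carry the instruction "Skip if you did not receive or view Ira". Q5 is skipped only by parents who did not receive Ira.
- The 20 STAI state items are last: "Q6. Self-evaluation questionnaire. Rate the following statements how they apply to you".

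D(3) states that parents are not blinded. It randomizes families, and gives a survey to each parent who consented and is present, so one family may return two. Section H names a t-test for the mYPAS and a descriptive summary of the parental survey. It names no between-arm STAI test and no unit of analysis.

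**The concern.** The STAI state items ask how a parent feels at that moment, and the parent knows the arm. What the parent has just been asked is therefore part of the measurement conditions, and those conditions should be the same in both arms. Here they are not.

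Parents who viewed Ira have just reported on it, and Q1 invites them to say whether it reduced their own stress. Control parents have in effect passed over the same block. If the block moves STAI answers at all, the movement is tied to arm and appears in the result as a PIRA effect or hides one. The survey is given only on the day of surgery, so there is no earlier STAI score to check against.

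**Working it through.** The plan gives no sample size, power or effect size for the STAI, so there is no stated figure to reproduce. The main point is settled by following each type of parent through Appendix B.

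| Before the STAI | Control parent | PIRA parent who viewed Ira | PIRA parent who did not view Ira |
|---|---|---|---|
| Introduction | read | read | read |
| Demographics (4) | answered | answered | answered |
| Q1 (16 statements) | 1 can be true: no link received | several can be true, including one on own stress | link received but not watched, or watched by someone else |
| Q2 (time spent) | not viewed | a time band | not viewed |
| Q3 (recommend) | skip | slider | skip |
| Q4 (missing topics) | skip | free text | skip |
| Q5 (suggestions) | skip | free text | open |
| Ira items open to the parent | 2 | 5 | 2 or 3 |

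1. The introduction and demographics are the same for everyone and cannot create an arm difference by themselves.
2. The difference arises in Q1 to Q5. It follows arm and, within the PIRA arm, viewing.
3. Under the printed order no control parent answers the Ira items in substance, and no PIRA viewer reaches the STAI without having met them. Order does not vary within an arm, so the data cannot separate an order effect from a PIRA effect. Comparing viewers with non-viewers does not help, because viewing is itself the exposure.

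**Minor note on the unit of analysis.** This applies only if a later STAI test pooled all surveys as independent, which section H does not say. Inputs:

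- 30 analysable families per arm (section I).
- Assumed fraction f of families returning two surveys: 0.10 to 0.50.
- Assumed within-couple correlation r: 0.3 to 0.5.

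Surveys per arm: N = 30(1 + f). True over naive variance: V = (N + 2r × 30f)/N. Actual level of a nominal 5% test: 2(1 − Φ(1.96/√V)).

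| f | N | V (r = 0.3 / 0.5) | Actual level |
|---|---|---|---|
| 0.10 | 33 | 1.05 / 1.09 | 5.6% / 6.1% |
| 0.25 | 37.5 | 1.12 / 1.20 | 6.4% / 7.4% |
| 0.50 | 45 | 1.20 / 1.33 | 7.4% / 9.0% |

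Example: f = 0.50 and r = 0.5 give V = (45 + 15)/45 = 1.33. Then 1.96/√1.33 = 1.70, which is a two-sided level of 9.0%.

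**The case against.** The strongest reply is that no effect has been shown. The documents contain nothing on question order and the STAI, parents know their arm whatever the order, and the outcome is secondary in a pilot powered on the mYPAS. Control parents also see all 16 statements of Q1, including those about stress, and a PIRA parent who did not view Ira follows nearly the same path as a control. All of this stands. It means that the size is unknown and that the difference lies in what is answered rather than in what is printed. It does not make the lead-in equal for controls and for PIRA parents who used the tool.

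A second reply is that the present order protects the primary outcomes. Utilization, recommendation and gaps come from this survey, and parents may leave items blank. Those outcomes are descriptive, so lost or coloured answers would be a real cost even without an arm contrast. This is a fair trade-off, but a small one: the survey is short.

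A reader might infer that the order favours PIRA, since Q1 lets a parent report only reduced stress of their own. The documents do not support a direction. Q1 also offers statements that Ira was hard to use or made the experience worse, and Q4 and Q5 ask for shortcomings. A reader might also infer that the form unblinds parents, but D(3) already leaves them unblinded. Nor does section H say that two parents' surveys are pooled; it is silent, and the case for 10% to 50% of families returning two surveys is an assumption.

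**Conclusion.** The point holds as a design weakness in one secondary outcome. The lead-in to the parental STAI differs by arm, and any shift it causes could not be separated from a PIRA effect after collection. This rests on the printed order in Appendix B; no section describes a different order or a branched form for controls. Neither size nor direction can be given.

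The child mYPAS comparison and its sample size, the PAED and program-logged utilization are not touched. The unit of analysis is a side note about missing detail. The 5.6% to 9.0% range depends on the assumed inputs and on pooling that the plan does not state, and at a 10% share of two-survey families the effect is small (5.6% to 6.1%). Two surveys per family would not in themselves bias the arm difference.

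**What to change.** Place the STAI first in Appendix B, before the introductory text on the arms and before every Ira item. Split the introduction so that the sentence allowing parents to leave questions blank stays above the STAI and still covers it. The demographic questions are the same in both arms and can follow.

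The cost is reordering one REDCap form. The downside is that 20 anxiety items then come before the primary survey items and may slightly affect their completion or tone. Those items are answered in substance in the PIRA arm only, so the change creates no between-arm difference in them. The change removes the arm-dependent lead-in, not the effect of parents knowing their arm.

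Separately, when section H comes to name a between-arm STAI comparison, it should respect the randomized family as the unit, either with family-clustered standard errors or with one parent per family chosen by a stated rule.
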